1. 29 subjects receiving Continuous Lumbar Epidural Analgesia (Patient-Controlled Epidural Analgesia- PCEA groups)
2. 29 subjects receiving IV PCA

Subjects will be randomly assigned one of the study groups either PCEA or IV PCA. Randomization protocol will be prepared according to level of the spinal fusion levels (1-3).

Study Interventions – The intervention to be evaluated in this study is epidural analgesia using an infusion of 0.0625% bupivacaine plus fentanyl 2mcg/ml. The Patient Controlled Epidural Analgesia (PCEA) pump will be programmed with the following settings:

- Bolus dose 5ml following emergence from general anesthesia (after clinical neurologic exam)
- Infusion 6-10 ml/hour; 2ml demand bolus every 20 minutes
- Max dose set for infusion over 4 hours + 6 boluses (12ml)
(Example - infusion 5ml/hr.; max 32ml over 4 hours)

This infusion will continue into the post-operative period. The epidural infusion will be continued until it is appropriate to transition the patient to a regimen of oral pain medications. This is typically determined by the surgical team, and the Acute Pain Service (APS). Duration of epidural catheter will be 72 hours a postoperatively. The APS will discontinue the epidural infusion and remove the epidural catheter per standard protocol.

For subjects in the IV PCA group, the intervention will include post-operative IV PCA with Hydromorphone (PCA syringe 25 mg/50 mL; dose range is 0.05mg - 0.4 mg which may be change according to patient's body habitus, age, etc.).

Epidural catheters will be placed by the spine surgeon under direct visualization intra-operatively prior to closing the surgical incision. Intra-operative epidural catheter placement by the spine surgeon will typically be done at the upper end of the dural exposure/laminectomy and the catheter will be pushed cephalad 5-10cm up the epidural space. For safety reasons, the subjects with dura damage during surgery will be excluded from the study because unpredictable amounts of the local anesthetic might reach the intrathecal space.

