Epidurals will be assessed for efficacy/function in the recovery room post-operatively by the APS, and then daily on the floor post-operatively (unless contacted by the floor nurse regarding specific concerns). Subjects are assessed for sensory function provided by the epidural (typically by sensation to cold or sharp), motor function, and any side effects or complications from the epidural. Motor block will be quantified with the Bromage scale (0 _ free movements of legs and feet, 1 _ just able to flex the knees with free movement of the feet, 2 _ unable to flex the knees but with free movement of the feet, and 3 _ unable to move legs or feet). Subjects will be asked about sensory deficits and graded on scale 1 to 3 (1 intact sensation, 2_ partial sensation, and 3_ complete sensation lost).

Visual analog pain scale (VAS) will be used to evaluate degree of pain at, 24, 48, and 72 hours after surgery. If a subject reports inadequate pain control with an epidural and the APS deems the epidural to be non-functional or non-efficacious, then the catheter may be removed and the patient may be changed to an IV PCA at that time.

Additionally, both the IV PCA and the epidural PCEA groups may be given additional “rescue” pain medications as needed in the recovery room, and these may be continued through the post-operative period on the floor. Current standard of care is using multimodal analgesia including acetaminophen, COX-2 specific inhibitors, dexamethasone, etc. These rescue medications may include, but are not limited to: pregabalin, gabapentin, methocarbamol, oxycodone, hydrocodone, methadone, and acetaminophen.

Total study duration is approximately 50 days, which starts from operating room admission for spinal fusion surgery to the first follow-up visit after discharge. Postoperative data will be collected during hospital stay and at the first follow-up visit.

4. Study Procedures:

Monitoring:

Standard intraoperative monitoring (EKG, blood pressure, pulse oximetry, end-tidal carbon dioxide, and temperature) and anesthetic care will be used in both groups.

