- Total use of post-operative oral opioid consumption during hospital stay on postoperative day 3.
- Total use of breakthrough medication on postoperative day 3.
- Patient satisfaction score at the last infusion day or postoperative day 3 or at discharge if patient discharged before POD3.
- Delirium during the hospital stay. Patients will be assessed baseline (preop) and daily during epidural or IV infusion , and the 6-week follow-up using the Confusion Assessment Method (CAM) and the Mini-Cognition assessment.
- Epidurals will be assessed for efficacy/function in the recovery room post-operatively by the Acute Pain Service, and then daily during infusion days (24, 48, and 72 hours)
- Length of hospital stay.
- Nausea, vomiting and antiemetic use for postoperative 72 hours
- Time to first bowel movement after surgery
- Wound infection rates during hospital stay
- Time to first ambulation after surgery
- Adverse effects include nausea, vomiting, pruritus, drowsiness, respiratory depression, and headache etc.

Data collection during 6-week follow-up visit (approximately postoperative 50 days):

- VAS Score

- HADS
- Pain evaluation with McGill short form questionnaire
- Patient satisfaction with post-operative analgesia
- Readmission rates within 30 days of surgery
- Wound infection rates until the first follow up visit

5. Criteria for Inclusion of Subjects:

- Adult subjects aged 18 years or older
- Scheduled for elective posterior lumbar spinal fusion surgery between 1 and 3 levels

6. Criteria for Exclusion: Patients will be excluded if they have:

- Baseline cognitive deficits sufficient to make objective pain self-assessments unreliable in the estimation of the Study Investigators.
- Immunocompromised subject
- Coagulopathy
- Severe liver and renal dysfunction
- Preoperative neurological deficits
- The dura damage during surgery
- Inability to follow directions or comprehend the English language.
- Females who are pregnant
- Prisoners.
- Patient refusal to provide informed consent.
 - Allergy to amide local anesthetics (lidocaine, bupivacaine, ropivacaine) Fentanyl allergy if the subject assigned epidural analgesia
 - Hydromorphone allergy if the subject assigned IV PCA

7. Sources of Research Material

- Patient information including name, medical record number, Date of Birth, and contact information including phone number.
- Weight, height, BMI, medical and surgical history, Medication list
- Pain Scores

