There is possibility of a non-working epidural catheter, infection, damage to nerves, arteries, and veins. An inadvertent placement of epidural catheter may result in systemic toxicity of local anesthetics (bupivacaine) inadequate pain relief, or epidural hematoma with neurological complications. Other side effect of epidural catheter placement includes dural puncture which may cause spinal headache. Epidural catheter will be placed by the surgeons under direct visualization at the end of the surgery. The surgical wound will be closed after ensuring the surgical field is dry and the catheter is not in the subarachnoid space. Subjects with dura damage during surgery will be excluded from the study.

1-Infection

Epidural catheter may cause infection such as meningitis. The incidence is very rare and increased after the 3 days of the epidural catheter placement. Infection will be monitored during postoperative period per hospital protocol. High risk subjects such as immunocompromised will not be enrolled to the study.

2-Local anesthetic (bupivacaine) toxicity

There is minimal risk of local anesthetic (bupivacaine) toxicity due to inadvertent injection of local anesthetic into the blood vessel. If injected into a blood vessel, large amounts of local anesthetic (bupivacaine) can cause tinnitus, lightheadedness, dizziness, tachycardia, blurred vision, and numbness around mouth, seizures, hypotension, and even cardiac arrest. If it happens appropriate supportive treatment will be given. The risk is high as the local anesthetic is infused in the raw surgical area that is hyperemic. The epidural catheter will be placed by an experienced surgeon under direct visualization and bupivacaine will be given a small amount via automatic pump, therefore the risk is minimal. The surgical wound will be closed after ensuring the surgical field is dry and the catheter is not in the subarachnoid space.

3- Bleeding and Epidural Hematoma

STU092016-061, [name], FormA-ResearchProtocol, Mod_24, 03-28-22

Page 7 of 11

Version 9, 12/11/2020

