Epidural catheter placement may cause epidural bleeding and hematoma. There is also possibility of neurological damage as a consequence of epidural hematoma. Epidural catheter placement in patients with a history of use of anti-coagulant or anti-platelet therapies will be done following the American Society of Regional Anesthesia and Pain Medicine (ASRA) current guidelines—“Regional Anesthesia in the Patient Receiving Antithrombotic or Thrombolytic Therapy: American Society of Regional Anesthesia and Pain Medicine Evidence-Based Guidelines”. Additionally, epidural catheters will be removed by the Acute Pain Service per protocol regarding patients who receive anti-coagulant or anti-platelet therapies post-operatively. These guidelines are followed to minimize the risk of epidural hematoma.

4- Risk of Epidural Opioid (Fentanyl):

Epidural fentanyl may cause common side effects of opioids including nausea, vomiting, pruritus (itching), drowsiness, urinary retention, and constipation. It may also decrease in breathing frequency (breathing rate <8 times/min), but low doses of fentanyl will be given very slowly and continuously. Because the doses of fentanyl will be given very low and investigators don't expect a decrease in the amount of respirations. The advert injection of fentanyl causes decreasing level of consciousness, hypotension, and respiratory depression.

5-Risk of Epidural Bupivacaine

Epidural bupivacaine may cause transient numbness or weakness, paralysis of lower extremities. Some degree of numbness and paresthesia expected but not motor block. Bupivacaine will be used low dose (0.0625%) to prevent development of motor block.

- Risk of IV Patient-Controlled Analgesia:**

IV patient-controlled opioid analgesia is part of the standard treatment for post-operative pain after surgery. Patient will receive baseline infusion and additionally opioid as needed.

1-Risk of Intravenous Catheter:

If the intravenous cannula is not placed correctly, it may cause rupture of vessels and blood leaks into the surrounding tissue. Using this misplaced cannula also causes extravasation of IV fluid and the drug, which leads to edema, tissue damage, and pain. There is risk of insertion site infection which may lead phlebitis, cellulitis and even sepsis.

2-Risk of Hydromorphone:

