Hydromorphone has side effects including nausea, vomiting, difficulty in urination, pruritus (itching), drowsiness, and constipation. It may also cause sedation and respiratory depression but low doses will be given very slowly and continuously.

- Psychological Stress**

Some of the questions related to the study may make the subject feel uncomfortable. Subjects may refuse to answer any of the questions, or take a break or stop participation in the study at any time.

- Loss of Confidentiality**

Any time information is collected; there is a potential risk of loss of confidentiality. Every effort will be made to keep subjects information confidential and secure as detailed below.

10. Costs to the Subject - We foresee no additional costs to the subjects. IV PCA is standard of care and epidural analgesia has been used for selected spine surgery cases at Zale University Hospital as a treatment option for postoperative pain management.

11. Subject Safety and Data Monitoring:

Since this is a single center study involving standard analgesic techniques, there is no safety monitoring board for this protocol. Data will be evaluated at the completion of the study to determine the efficacy and safety of epidural analgesia relative to control. Protocol violations and adverse events will be recorded and reported to the IRB during the study.

All unexpected or serious adverse events will be reported to the UTSW IRB office within 24 hours of their discovery. The PI will review aggregated adverse events after 25 subjects have been enrolled.

12. Procedures to Maintain Confidentiality:

All subjects will be identified by a numerical code (case # 01, case # 02.... etc.) during gathering and reporting the information. Study records will be kept confidential as required by law. Federal Privacy Regulations provide safeguards for privacy, security, and authorized access. Except when required by law, subjects will not be identified by name, social security number, address, telephone number or any other direct personal identifier in study records disclosed outside of the UT Southwestern Medical Center. All research records will be locked in offices in the Departments of Anesthesiology and Pain Management, and Neurosurgery, , or stored on secure UT Southwestern computer servers. Only research staff listed as key personnel will be able to access these records.

13. Potential Benefit:

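### Safety data are not collected alike in the two arms, and the 6-week visit does not ask about late neurological or catheter-infection events

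*Combined protocol and SAP*

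**What the plan says.** **In hospital, both arms.** Section 4 (Postoperative data collection during hospital stay) has one general adverse-effect item, an open list: "Adverse effects include nausea, vomiting, pruritus, drowsiness, respiratory depression, and headache etc". Nausea, vomiting and antiemetic use over 72 hours, wound infection and delirium are separate items.

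**In hospital, epidural.** Section 3 (Study Interventions) has the Acute Pain Service assess epidurals in the recovery room and then daily. The assessment covers sensory function, "motor function, and any side effects or complications from the epidural". It adds that "Motor block will be quantified with the Bromage scale" (0 to 3) and that sensory deficits are graded 1 to 3. Section 4 places the daily checks on infusion days, at 24, 48 and 72 hours.

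**After discharge.** The 6-week list in Section 4 (visit at about day 50) has VAS, HADS, the McGill short form, satisfaction, "Readmission rates within 30 days of surgery", and wound infection up to the visit. The delirium item adds CAM and Mini-Cog at 6 weeks.

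**Named risks.** Section 9 names meningitis, epidural haematoma with neurological damage, nerve damage, local anaesthetic toxicity, spinal headache and urinary retention. It also says: "Epidural bupivacaine may cause transient numbness or weakness, paralysis of lower extremities".

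**Oversight.** Section 11 has no safety board and foresees a safety evaluation against control at completion. The principal investigator reviews aggregated adverse events after 25 subjects. It also says: "Protocol violations and adverse events will be recorded and reported to the IRB during the study". Section 4 says that investigators are not blinded.

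**The concern.** A comparative statement about safety needs the same question, asked in the same way and over the same period, in both arms. Here the most detailed in-hospital enquiry belongs to one arm. At the visit where lasting harm would show, neither arm is asked about it.

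Two problems follow. In hospital, a difference between arms in numbness, weakness or complications would partly reflect who was examined. After discharge, a persistent deficit or headache that led to no readmission would reach the record only if the patient volunteered it or a clinician passed it on. Both the final evaluation and the review after 25 subjects can use only what was recorded. The report could then state that few or no late complications occurred when the plan had not asked about them.

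**Working it through.** **1. Where each named risk is picked up.** This sets the risks named in Section 9 against the collection described in Sections 3, 4, 9 and 11.

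| Risk | In hospital, PCEA | In hospital, IV PCA | 6-week visit |
|---|---|---|---|
| Nausea, vomiting, pruritus, drowsiness, respiratory depression | Listed | Listed | No item |
| Headache | Listed | Listed | No item |
| Numbness, weakness, paralysis | Sensory grade, Bromage | None described | No item |
| Nerve damage, haematoma with neurological damage | Sensory, motor and complication checks | None described | Only through 30-day readmission |
| Meningitis, other catheter infection | Complication check; hospital infection monitoring | Not applicable to a catheter; no meningitis item | Only through wound infection or 30-day readmission |
| Urinary retention | Complication check or open list | Open list only | No item |

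The general duty in Section 11 to record adverse events applies to every cell. It names no question, visit or form.

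The first two rows are symmetric in hospital. The asymmetry lies in the neurological and complication rows, and the missing late enquiry affects all rows.

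**2. Length of the unasked period.** The last scheduled epidural check is at 72 hours (day 3) and the visit is at about day 50: 50 − 3 = 47 days. If the visit falls at exactly six weeks (6 × 7 = 42), the interval is 42 − 3 = 39 days. Readmission is counted to day 30, which leaves 50 − 30 = 20 days uncounted (42 − 30 = 12 at six weeks). These are lengths of time, not measures of bias.

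**3. What 29 per arm could show with complete collection.** The sample size in Section 14 is set for the primary pain outcome, and it reproduces. A two-sample t-test with d = 0.8, one-sided 0.025 and 80% power needs 26 per arm, or 52 (power 80.75%). Then 52 / 0.9 = 57.8, rounded up to 58, or 29 per arm. The plan gives no figure for safety.

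- If 0 of 29 have an event, the one-sided 95% upper bound is 1 − 0.05^(1/29) = 9.8%. With 26 it is 1 − 0.05^(1/26) = 10.9%.
- The chance of at least one event in 29 is 1 − (1 − p)^29. The documents give no event rates, so p is assumed:

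| Assumed p | Chance of at least one event |
|---|---|
| 0.1% | 2.9% |
| 1% | 25.3% |
| 2% | 44.3% |
| 5% | 77.4% |

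No formal comparison of rare complications is possible. Any single case is therefore informative, which is a reason to ask for it and report it descriptively.

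**The case against.** The strongest reply is that the plan collects more than the six-item list suggests. Much of that stands.

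- **A reader might infer that adverse effects are collected only in hospital and that the 6-week visit asks for no safety data.** The documents do not support this. Wound infection, 30-day readmission and CAM/Mini-Cog are follow-up safety items. Section 11 records adverse events throughout and has serious or unexpected events reported within 24 hours of discovery. Section 9 adds infection monitoring under hospital protocol. A serious haematoma or infection would probably surface this way. These routes are partly passive, however, and do not solicit milder or lasting symptoms.
- **A reader might infer that numbness and weakness are left to the open end of the list.** They are not, for PCEA subjects in hospital: Section 3 measures both. What is missing is an IV PCA counterpart and a late check. The Bromage and sensory sentences do not name an arm and could be meant for everyone, but they stand in a paragraph about assessing epidurals. If both arms are meant, the plan should say so.
- **A reader might infer that the comparison tilts towards PCEA, because five of the six listed effects are opioid effects.** This is not established. PCEA subjects receive fentanyl, and Section 4 says both groups receive hydromorphone. Section 2 reports more drowsiness and headache with PCEA in a cited comparison. Closer checks of epidural subjects by unblinded staff could raise PCEA counts, while the missing late enquiry could lower them.
- **A reader might infer that checks stop just where catheter infection risk begins.** Section 9 says: "The incidence is very rare and increased after the 3 days of the epidural catheter placement". Section 3 says: "Duration of epidural catheter will be 72 hours a postoperatively". The first sentence can equally mean that risk grows with dwell beyond three days, which the second would limit. The point does not depend on either reading.

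It is also fair that case-report forms are not among the documents, so a form might ask more than the protocol says. Safety is neither the primary outcome nor the secondary outcome named in Section 1.

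**Conclusion.** The concern holds in a limited form. As written, the plan has no structured adverse-event collection that is the same in both arms and runs to the follow-up visit. In-hospital neurological and complication counts are not comparable between arms. Late events that lead to neither wound infection nor readmission within 30 days can be missed over an interval of about 47 days (39 if the visit is at exactly six weeks). The net direction of any bias is uncertain, and its size cannot be computed from the documents.

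The primary analysis is unaffected. What is weakened is the safety evaluation promised in Section 11. This rests on reading the Section 3 checks as belonging to the epidural arm, and on the case-report forms asking no more than the protocol describes. The change is a cheap improvement worth making.

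**What to change.** 1. Write one fixed adverse-event checklist from the risks Section 9 already names, including motor and sensory status. Use it identically in both arms at the in-hospital assessments.
2. Use the same checklist at the existing 6-week visit. Ask both arms about new weakness or numbness, persistent headache, bladder symptoms, and meningitis or epidural infection since discharge.
3. At that visit, record any readmission or unplanned care since discharge, with date and cause. Keep the 30-day readmission rate as defined.
4. State in Section 14 that these events will be reported descriptively by arm, because 29 per arm cannot compare rare events.

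The cost is a slightly longer form, motor and sensory questions for IV PCA subjects, and more minor events recorded in both arms. No extra visit is needed.

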Surgical and anesthetic technique: All subjects will undergo a standardized general anesthetic for the operative procedure (see Appendix 1). The surgery and postoperative management will also be standardized. The difference between patient cohorts will be the use of epidural vs. intravenous analgesia for post-operative pain management. Both study groups will receive hydromorphone, which is a standard of care drug for post-operative pain. If the subject has a documented allergy or intolerance to hydromorphone, then a different opioid may be substituted in either the IV PCA or the epidural drug solution. The epidural study group will also receive Bupivacaine (local anesthetic) in combination with fentanyl. The intervention being tested in the current study is the route of analgesic medication—intravenous or epidural,

as well as the addition of bupivacaine in the epidural analgesic group. Note that bupivacaine contraindicated for intravenous use, and may have significant cardiac and neurologic sequelae if given intravenously. Therefore, it will be included only in the epidural analgesia group.

Epidurals that are evaluated and felt to be non-efficacious will be removed, and the subject will be changed to intravenous hydromorphone PCA. These subjects will be statistically analyzed primarily by intent to treat method, with possible secondary analysis, to be analyzed in an 'as treated group'. Investigators will not be blinded to treatment allocation due to the nature of the intervention. Subjects will be randomized to receive IV PCA or epidural PCEA.

The following **variables** will be evaluated to determine differences between Epidural Analgesia and Standard Care:

Preoperative Data Collection during preoperative outpatient clinic visit or preoperative period before the surgery

- VAS score
- Baseline delirium assessment (the Confusion Assessment Method (CAM) and the Mini-Cognition assessment (MiniCog)
- Hospital anxiety depression scores (HADS) will be evaluated- baseline (preop)
- Pain will also be evaluated with McGill short form questionnaire-baseline (preop).

Postoperative data collection during hospital stay:

- Post-operative Visual Analogue Pain (VAS) Score within 3 hours or PACU discharge, postoperative 24, 48, and 72 hours during infusion days (± 2 hrs.) after surgery (Primary endpoint: VAS Score at 24h).
- Post-operative intravenous opioid consumption for postoperative days 1, 2, and 3 (converted to Morphine Equivalents).

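### Two allergy exclusions depend on the assigned arm; the hydromorphone one also contradicts Study Procedures, and no analysis rule covers subjects removed this way

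*Combined protocol and SAP*

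**What the plan says.** Section 6 (Criteria for Exclusion) ends with two conditional items: "Fentanyl allergy if the subject assigned epidural analgesia" and "Hydromorphone allergy if the subject assigned IV PCA". Section 8 (Recruitment Methods and Consenting Process) has subjects checked against the exclusion criteria before they are approached. No section says when randomisation takes place relative to the allergy check.

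Section 4 (Surgical and anesthetic technique) treats hydromorphone differently. It says "Both study groups will receive hydromorphone, which is a standard of care drug for post-operative pain". For allergy or intolerance to that drug, "a different opioid may be substituted in either the IV PCA or the epidural drug solution". When an epidural is judged not to work, "the subject will be changed to intravenous hydromorphone PCA". Section 3 (Study Interventions) gives the epidural solution without hydromorphone: "The intervention to be evaluated in this study is epidural analgesia using an infusion of 0.0625% bupivacaine plus fentanyl 2mcg/ml".

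On who is analysed, Section 4 says of the subjects with failed epidurals: "These subjects will be statistically analyzed primarily by intent to treat method", with an as-treated analysis as a possible secondary. Section 14 (Biostatistics) names no analysis population. It allows for 10% loss before surgery is completed, which takes 52 subjects to 58.

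**The concern.** Randomisation makes the arms comparable when the same people could have entered either one. Under Section 6, a fentanyl-allergic subject stays if assigned IV PCA and leaves if assigned epidural. A hydromorphone-allergic subject does the reverse. The subjects left in the two arms are then selected by different rules.

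Section 4 adds a second uncertainty. If hydromorphone-allergic subjects are kept by substitution, the fentanyl rule acts alone and nothing offsets it. The text does not settle which reading applies. Nor does it say whether a subject removed for allergy after assignment counts in the 24-hour VAS comparison. Investigators are not blinded, so that choice could be made by people who know the allocation.

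**Working it through.** **The passages side by side**

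| Allergy | Assigned epidural | Assigned IV PCA |
|---|---|---|
| Fentanyl, Section 6 | excluded | not excluded |
| Fentanyl, Section 4 | no rule | no rule |
| Hydromorphone, Section 6 | not excluded | excluded |
| Hydromorphone, Section 4 | substitute allowed | substitute allowed |

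- The rows for each drug under Section 6 differ between columns, so neither criterion can be applied until the arm is known. Screening before approach cannot do that.
- The two hydromorphone rows contradict each other for IV PCA. Confining that exclusion to IV PCA also does not match Section 4, where both groups receive the drug and failed epidurals move to it.
- Section 4 speaks of replacing hydromorphone in the epidural solution. The solution in Section 3 is bupivacaine plus fentanyl, so there is none in it to replace.
- Section 4 has no rule for fentanyl allergy. The contradiction therefore concerns hydromorphone only.

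**The plan's own figures**

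Inputs from Section 14: d = 0.8, one-sided alpha 0.025, power 80%, two equal arms. The two-sample t test needs 25.52, so 26 per arm and 52 in all. Allowing for loss, 52 / 0.90 = 57.8, so 58. Both stated figures reproduce.

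Power at d = 0.8 is 0.849 with 29 and 29 analysed, 0.843 with 28 and 29, 0.807 with 26 and 26, and 0.791 with 25 and 25. The margin is 58 − 52 = 6 subjects from all causes. Sample size is not the difficulty.

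**Possible size of the bias (assumed inputs)**

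The documents give no allergy rate and no link between allergy and pain. I assume that a fraction f of subjects is fentanyl-allergic and that their 24-hour VAS differs by s SD.

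For f between 1% and 10%, the expected number per 29 is 29f = 0.29 to 2.9. The chance of at least one in an arm is 1 − (1 − f)^29 = 0.25 to 0.95.

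Suppose these subjects are removed from the epidural arm only, there is no treatment effect, and nothing offsets the removal. The IV PCA mean then exceeds the epidural mean by f × s. With one in 29 removed, the arms are 28 and 29:

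- noncentrality = f × s × √(28 × 29 / 57) = f × s × 3.774
- degrees of freedom = 28 + 29 − 2 = 55; one-sided critical t = 2.004

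| s (SD) | f × s (SD) | Noncentrality | One-sided type I error |
|---|---|---|---|
| +0.5 (worse pain) | 0.017 | 0.065 | 0.029 |
| +1 (worse pain) | 0.034 | 0.130 | 0.033 |
| −0.5 (better pain) | −0.017 | −0.065 | 0.021 |
| −1 (better pain) | −0.034 | −0.130 | 0.018 |

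The larger shift is 0.034 / 0.8 = about 4% of the design effect. At f = 1%, type I error is 0.026 to 0.027 with worse pain and 0.024 to 0.023 with better pain.

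A simulation of 29 per arm gives the same pattern. With one subject per 29 having each allergy and Section 6 applied in both arms, the removals cancel and the error stays at 0.025. With hydromorphone-allergic subjects kept under Section 4, it is 0.029 to 0.033 with worse pain and 0.021 to 0.019 with better pain.

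**The case against.** The strongest reply is that this may never happen. Section 8 checks exclusions before approach, and Section 7 lists medical history and medications as source data, so allergies could be known early and dealt with before assignment. No removal after assignment is shown. This stands as a limit on the claim. It does not remove the problem, because the two items are worded to take effect by arm, and nothing says both are applied to every candidate in advance.

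A second reply is that the effect is negligible. The 0.033 needs about 3.4% fentanyl allergy and a full 1 SD difference in pain, both assumed. This also stands. The figures bound the issue; the point rests on the contradiction and the unsettled rule.

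A third is that the plan does state intent to treat, and for failed epidurals, a group that matters for 24-hour pain. That is right, and a reader who inferred that the plan has no intent-to-treat provision would be wrong. The gap is narrower: subjects excluded after assignment for allergy. The 10% allowance does not fill it, because it sets how many are randomised and not who is analysed.

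A reader might also extend the point to dura damage during surgery. That exclusion is worded without reference to arm, and the documents give no ground for saying that it biases the contrast. How missing 24-hour scores are handled is likewise a separate question.

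**Conclusion.** The point holds in a limited form. Section 6 makes two exclusions depend on the assigned arm, the hydromorphone one contradicts Section 4, and no analysis rule covers subjects removed under either.

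A reader might infer that the primary comparison is materially biased towards epidural analgesia. The documents do not support that. The number affected may be zero, the direction depends on whether allergic subjects have more or less pain, and the two removals can offset. Under the assumed one in 29 with a 0.5 to 1 SD difference and no offset, one-sided type I error lies between 0.018 and 0.033 against a nominal 0.025. At 1% it lies between 0.023 and 0.027.

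I rate it between minor and should-fix: the likely effect is small, but the rule is wrong as written and cheap to repair.

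**What to change.** 1. Reconcile Sections 3, 4, 6 and 8 on fentanyl and hydromorphone allergy, including the mention of hydromorphone in the epidural solution. Whether an allergy leads to exclusion or substitution is the sponsor's clinical decision.
2. Add to Section 6: *Any exclusion for allergy is settled before randomisation and applied identically to all candidates, whichever arm they may receive.* This binds exclusions only. A substitution rule, if chosen, may still refer to the drugs of each arm.
3. Carry the intent-to-treat statement from Section 4 into Section 14: *All randomised subjects with a 24-hour VAS are analysed in their assigned arm. Any exclusion after assignment is reported by arm and reason.* This does not settle how subjects without a 24-hour score are treated, so item 2 is the main safeguard.

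The cost is amendment wording and a short table. A few candidates may be screened out before randomisation who could have entered one of the arms. Sample size and treatment are unchanged.
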